7.9.2 Clinical Laboratory Parameters

For each quantitative clinical laboratory parameter, descriptive statistics of the observed values (in derived SI units) as well as change from study baseline will be presented overall for each assessment timepoint for the safety population.

Parameter values will also be categorized as low, normal, or high based on reference ranges provided by the lab, and shifts from baseline to each later timepoint will be tabulated. If there is more than one measurement for a lab parameter at a postbaseline timepoint, only the last measurement will be used.

Listings of laboratory parameters will be included.

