7.9.5 Additional Vital Signs Parameters

Vital signs evaluations at each assessment timepoint not included in the PD analyses (ex. standing blood pressure and pulse assessments) and the corresponding change from study baseline will be summarized for each treatment group and presented in a data listing.

The number and percentage of patients who had a notable change from baseline in BP and pulse (based on the criteria in [Table 4](#)), will be presented by treatment group.

Table 4. Criteria for Notable Changes in Post-Baseline Vital Signs

Vital Sign Parameter	Flag	Criteria*	
		Observed Value	Change from Study Baseline
Supine/Standing Systolic Blood Pressure (mmHg)	High	≥ 180	Increase of ≥ 30
	Low	≤ 90	Decrease of ≥ 30
Supine/Standing Diastolic Blood Pressure (mmHg)	High	≥ 105	Increase of ≥ 20
	Low	≤ 50	Decrease of ≥ 20
Supine Pulse Rate (bpm)	High	≥ 110	Increase of ≥ 20
	Low	≤ 50	Decrease of ≥ 20
Standing Pulse Rate (bpm)	High	≥ 120	Increase of ≥ 25
	Low	≤ 50	Decrease of ≥ 20

*A postbaseline value is considered as a notable value if it meets both criteria for observed value and change from baseline.

Orthostatic BP Measurements

Orthostatic changes in systolic BP, diastolic BP, and pulse will be summarized for each treatment group. An orthostatic measurement is obtained by subtracting the supine measurement from the standing measurement.

The number and percentage of patients who meet the following criteria at any postdose timepoint will also be summarized by treatment group:

- Orthostatic decrease in systolic BP of > 20 mmHg from supine to standing
- Orthostatic decrease in diastolic BP of > 15 mmHg from supine to standing
- Orthostatic increase in pulse of > 30 beats per minute from supine to standing

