9. DATA HANDLING CONVENTIONS

9.1 REPEATED OR UNSCHEDULED ASSESSMENTS OF SAFETY PARAMETERS

If a patient has repeated safety assessments (e.g., for a lab parameter) prior to dosing of study drug, then the results from the final non-missing assessment made prior to the start of study drug will be used as baseline. If there is more than one safety measurement (e.g., for a lab parameter) at a postbaseline timepoint, only the last measurement will be used. All postbaseline assessments including unscheduled assessments, if any, will be used for notable value determination, and all assessments will be presented in data listings.

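### Repeated post-baseline lab and ECG results are tabulated by the last value only, so an abnormal result followed by a normal repeat appears as normal in the summaries and shift tables

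*SAP*

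**What the plan says.** SAP 7.9.2 plans descriptive statistics for each quantitative lab parameter and a low/normal/high classification, in which "shifts from baseline to each later timepoint will be tabulated". The next sentence sets the rule for repeats: "If there is more than one measurement for a lab parameter at a postbaseline timepoint, only the last measurement will be used". The section ends: "Listings of laboratory parameters will be included".

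SAP 9.1 makes the rule general: "If there is more than one safety measurement (e.g., for a lab parameter) at a postbaseline timepoint, only the last measurement will be used". It then adds a limit: "All postbaseline assessments including unscheduled assessments, if any, will be used for notable value determination, and all assessments will be presented in data listings".

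The only notable-value criteria are in SAP 7.9.5, Table 4 ("Criteria for Notable Changes in Post-Baseline Vital Signs"). The summary built on them is "The number and percentage of patients who had a notable change from baseline in BP and pulse". For orthostatic changes the same section plans "The number and percentage of patients who meet the following criteria at any postdose timepoint will also be summarized by treatment group".

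SAP 7.9.6 plans descriptive statistics for ECG parameters and a shift table of the overall interpretation (three categories) from study baseline to Day 15. Neither 7.9.2 nor 7.9.6 defines a notable value.

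**The concern.** A repeat test is often ordered because the first result looked wrong. Where that is so, keeping only the last value acts selectively: abnormal first results can be replaced by normal ones, while normal first results are seldom repeated and stand. The SAP avoids this for blood pressure and pulse by counting every post-baseline value. It has no equivalent for labs or ECGs, where the shift table is the only categorical display.

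Safety is a stated objective, and the schedule offers little redundancy. After dosing, the full chemistry, hematology, coagulation and urinalysis panels are drawn only on Day 15 and Day 42, and ECGs only 4 hours after the Day 1 morning dose and on Day 15. If a Day 15 panel value is replaced by its repeat, no other full panel close to treatment can show the abnormality. An arm with a real drug effect would probably have more results repeated, and so more replaced, which would draw the active and placebo shift tables together.

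**Working it through.** The plan gives no figure for this point, and SAP 4 says the sample size was set outside statistical considerations. The check is therefore a reading of the rules followed by an illustration.

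**Step 1. Which displays keep an abnormal value that is followed by a normal repeat at the same timepoint?**

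| Data | By-timepoint statistics | Categorical table | Listing |
|---|---|---|---|
| Labs | lost (7.9.2, 9.1) | lost from shift table | kept |
| ECG | lost (9.1) | lost from Day 15 shift table if the repeat is at Day 15 | kept |
| BP and pulse | lost under 9.1 where summarized as safety data | kept in notable-change counts (9.1, Table 4) | kept |

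A further route is open for all three. Under protocol 3.7.3.9, an abnormality that the Investigator considers clinically significant, or that needs intervention, is recorded as an adverse event. If treatment-emergent, it enters the tables of SAP 7.9.1.

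**Step 2. What is one patient worth?** Allocation is 26 patients at 5:5:3.

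- Active arms: 26 × 5/13 = 10 each, so one patient is 100/10 = 10.0 points.
- Pooled active, 20 patients: 100/20 = 5.0 points.
- Placebo: 26 × 3/13 = 6, so one patient is 100/6 = 16.7 points.
- All 26 patients: 100/26 = 3.8 points.

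The per-arm figures need tables by treatment group. Protocol 3.9.3.4.2 and SAP 6.1 plan these, although SAP 7.9.2 and 7.9.6 describe the descriptive statistics as presented overall.

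**Step 3. Illustration with assumed rates.** Let p be the share of patients whose first value is abnormal and is repeated, and q the share of those repeats that are normal. Neither is in the documents. The tabulated rate is p(1 − q) instead of p. The chance of losing at least one patient's abnormal result in an arm of 10 is 1 − (1 − pq)^10.

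| p | q | Tabulated rate | Worst-value rate | Chance of ≥ 1 lost in 10 |
|---|---|---|---|---|
| 0.10 | 0.30 | 0.07 | 0.10 | 1 − 0.97^10 = 26% |
| 0.10 | 0.70 | 0.03 | 0.10 | 1 − 0.93^10 = 52% |
| 0.30 | 0.30 | 0.21 | 0.30 | 1 − 0.91^10 = 61% |
| 0.30 | 0.70 | 0.09 | 0.30 | 1 − 0.79^10 = 91% |

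**Step 4. Upper bound for a numerical lab value.** Assume that every first value above the 97.5th percentile is repeated once, that first and repeat values are bivariate normal with correlation r, and that treatment shifts the mean by d standard deviations. Then P(first high) = 1 − Φ(1.96 − d), and P(tabulated high) = P(both values > 1.96).

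| d | P(first high) | P(tabulated high), r = 0.5 / 0.7 / 0.9 |
|---|---|---|
| 0.5 | 7.2% | 2.0% / 3.1% / 4.8% |
| 1 | 16.9% | 6.8% / 9.1% / 12.4% |

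In an arm of 10 the expected loss per parameter is 0.24 to 0.52 patients at d = 0.5 and 0.45 to 1.0 at d = 1. At r = 0.7 and d = 1, the active-minus-placebo difference falls from 14.4 to 8.2 points. The model gives the probability of a high value, not of a shift from a normal baseline. It does not apply to the ECG table, which classifies an overall interpretation.

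**The case against.** The strongest reply is that the trigger is assumed. The protocol's provisions for repeating out-of-range labs, ECGs, blood pressure and fasting glucose all serve eligibility. The one post-baseline repeat it prescribes is for a positive pregnancy test. If no lab or ECG is repeated after dosing, nothing is lost. The SAP also gives no lab visit windows, so a repeat on a later day may not belong to the same timepoint, in which case the first value stands. This objection stands: the direction of the bias is plausible, but its size cannot be fixed from the documents, and Step 4 is a ceiling.

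A reader might infer that abnormal values disappear for every safety test, or survive only in a listing. The documents support neither. Blood pressure and pulse keep their notable-change counts, and the orthostatic criteria apply at any postdose timepoint. Lab and ECG findings that are clinically significant or need intervention reach the adverse event tables if treatment-emergent, and 26 patients' listings can be read in full. The adverse event route is not wholly independent, however, because a normal repeat may itself influence the Investigator's judgment of significance.

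The rule is also formally symmetric: a normal value followed by an abnormal repeat is tabulated as abnormal, and baseline too is the last value before dosing. This helps only to the extent that normal results are repeated.

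Finally, a worst-value table has its own bias. The most extreme of several values, set against one baseline value, will show shifts by chance. That is a good reason to add such a table and not to substitute it for the planned one.

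**Conclusion.** The point holds for labs and, through SAP 9.1, for ECGs. An abnormal result with a normal repeat at the same timepoint leaves the descriptive statistics and the shift tables, and the all-assessments safeguard does not reach it because notable values are defined only for blood pressure and pulse.

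Each patient affected is worth 10 points in an active arm or 16.7 points in placebo. How many are affected depends on post-baseline retesting, which the documents do not describe. A lean toward normal follows only if repeats are prompted mainly by abnormal results.

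It would go too far to conclude that the safety results will be materially biased or that the last-value rule must be replaced. The rule is pre-specified, the values are not removed from the report, and any inferential statistics are for descriptive purposes only. Priority: CONSIDER.

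**What to change.** Keep the planned per-timepoint tables and the last-value rule for them. In SAP 7.9.2, 7.9.6 and 9.1, add a shift table by treatment group from study baseline to:

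- the worst post-baseline value of each lab parameter, separately for low and high;
- the worst post-baseline overall ECG interpretation.

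Use all post-baseline assessments, including repeats and unscheduled ones, and exclude only values that the laboratory or ECG reader declares invalid. This gives labs and ECGs what SAP 9.1 already gives blood pressure and pulse.

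The cost is a few sentences in the SAP, one derivation flag and the extra tables, and the change should be made before unblinding. The downside is that transient or spurious values will appear, and chance alone will overstate shifts in every arm. A footnote should say that the table is to be read as a comparison between arms, not as an absolute rate.

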7.9.3 Estimated Glomerular Filtration Rate (eGFR)

Change from study baseline in eGFR will be summarized by treatment group for each assessment day. eGFR (mL/min/1.73m²) will be calculated according to the Chronic Kidney Disease Epidemiology Collaboration (CKD-EPI) creatinine equation.(4)

$$GFR = 141 \times \min\left(\frac{sCr}{\kappa}, 1\right)^\alpha \times \max\left(\frac{sCr}{\kappa}, 1\right)^{-1.209} \times 0.993^{Age} \times 1.018 I_F \times 1.159 I_B$$

where sCr is serum creatinine (mg/dL),

κ is 0.7 for females and 0.9 for males,

α is -0.329 for females and -0.411 for males,

min indicates the minimum

max indicates the maximum

I_F is an indicator function for female patients

I_B is an indicator function for black patients

Boxplots of eGFR values will be presented for each treatment group and assessment day.

7.9.4 Urine Creatinine Ratio (UACR)

Change from study baseline in UACR will be summarized by treatment group for each assessment day. UACR will be calculated using the following equation:

$$UACR(\text{mg/g}) = \frac{\text{urine albumin (mg/dL)}}{\text{urine creatinine (g/dL)}}$$

Boxplots of UACR values will be presented for each treatment group.

7.9.5 Additional Vital Signs Parameters

Vital signs evaluations at each assessment timepoint not included in the PD analyses (ex. standing blood pressure and pulse assessments) and the corresponding change from study baseline will be summarized for each treatment group and presented in a data listing.

The number and percentage of patients who had a notable change from baseline in BP and pulse (based on the criteria in [Table 4](#)), will be presented by treatment group.

Table 4. Criteria for Notable Changes in Post-Baseline Vital Signs

Vital Sign Parameter	Flag	Criteria*	
		Observed Value	Change from Study Baseline
Supine/Standing Systolic Blood Pressure (mmHg)	High	≥ 180	Increase of ≥ 30
	Low	≤ 90	Decrease of ≥ 30
Supine/Standing Diastolic Blood Pressure (mmHg)	High	≥ 105	Increase of ≥ 20
	Low	≤ 50	Decrease of ≥ 20
Supine Pulse Rate (bpm)	High	≥ 110	Increase of ≥ 20
	Low	≤ 50	Decrease of ≥ 20
Standing Pulse Rate (bpm)	High	≥ 120	Increase of ≥ 25
	Low	≤ 50	Decrease of ≥ 20

*A postbaseline value is considered as a notable value if it meets both criteria for observed value and change from baseline.

Orthostatic BP Measurements

Orthostatic changes in systolic BP, diastolic BP, and pulse will be summarized for each treatment group. An orthostatic measurement is obtained by subtracting the supine measurement from the standing measurement.

The number and percentage of patients who meet the following criteria at any postdose timepoint will also be summarized by treatment group:

- Orthostatic decrease in systolic BP of > 20 mmHg from supine to standing
- Orthostatic decrease in diastolic BP of > 15 mmHg from supine to standing
- Orthostatic increase in pulse of > 30 beats per minute from supine to standing

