1. INTRODUCTION

1.1 BACKGROUND AND STUDY RATIONALE

The NO-sGC-cGMP (nitric oxide – soluble guanylate cyclase – cyclic guanosine 3',5'-monophosphate) pathway plays a critical role in the cardiovascular system. In the vascular endothelium, sGC is stimulated by NO to produce cGMP, which acts on downstream targets including cGMP-dependent protein kinases, phosphodiesterases, and ion channels. This leads to relaxation of the vascular smooth muscle and vasodilation. In addition, intracellular cGMP is involved in processes that affect vascular proliferation, fibrosis, and inflammation. Impaired NO-sGC-cGMP signaling, has been implicated in the pathogenesis of cardiovascular diseases such as systemic and pulmonary hypertension, coronary artery disease, congestive heart failure, peripheral vascular disease, atherosclerosis, and kidney disease. Agents that stimulate sGC to increase cGMP production (1,2) may be useful for treating and/or preventing a broad range of diseases that may ensue from dysfunction in the fundamental NO-sGC-cGMP pathway.(3,4)

This exploratory, proof-of-concept study will evaluate the safety, tolerability, PK, and PD of 2 dosing regimens of daily 40 mg IW-1973 administered orally for 2 weeks to patients with type 2 diabetes mellitus and hypertension. This study is designed to explore the tolerability profile of the MAD MTD, 40 mg IW-1973, in a patient population, and to explore whether tolerability can be improved with an initial week of BID dosing.

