3.5.3 Selection of Dosage in the Study

This Phase 2a exploratory study will evaluate 40 mg IW-1973 administered daily for 2 weeks according to 2 different regimens: QD for both weeks or BID for the 1st week and QD the 2nd week. In the Phase 1b MAD study ([ICP-1973-102](#)), 40 mg IW-1973 was considered the maximum tolerated repeat dose, therefore, 40 mg was chosen for evaluation in this patient population.

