7.9.1 Adverse Events

All adverse events (AEs) will be coded using the Medical Dictionary for Regulatory Activities (MedDRA) Version 19.1 and will be classified by MedDRA system organ class (SOC), and preferred term (PT).

Treatment-emergent adverse events (TEAEs) are those AEs that started or worsened in severity after the administration of study drug. If it is not possible to determine when the event started due to incomplete start dates/times, it will be assumed to be treatment-emergent.

The number and percentage of patients who experience at least one TEAE as well as those who experience each specific SOC and PT will be presented by treatment group as well as for IW-1973 overall using the Safety Population. TEAEs will also be summarized by week, where TEAEs that started during Week 1 (study days 1-7) or Week 2 (study days 8-14) will be presented by treatment group for the respective week. Summaries of study drug-related TEAEs will also be presented by treatment group. For presentation of AE incidence, AEs will be sorted alphabetically by SOC, and within each SOC, by decreasing incidence of PT in the overall group.

In addition, AEs in screen failure patients, TEAEs, severe TEAEs, study drug-related AEs (those that are determined by the Investigator to be related to study drug), serious AEs, AEs that resulted in study discontinuation, and AEs that resulted in death (if any) will be presented in separate listings.

Adverse Events of Clinical Interest

Since an increased risk for bleeding may represent a class effect with sGC stimulators, bleeding events and TEAEs related to bleeding will be summarized by treatment group and presented in a data listing. Similarly, TEAEs associated with hypotension or lowering of BP will be summarized by treatment group and presented in a data listing. See [Appendix 1](#) for details on the determination of the events for each category of interest.

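### Patient counts for orthostatic change, notable BP/pulse change and grouped hypotension events have no Week 1 window, although the active regimens differ only on Days 1-7

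*SAP*

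**What the plan says.** - **Question.** Protocol 1.1 gives as one purpose "to explore whether tolerability can be improved with an initial week of BID dosing". Protocol 2 states the formal objective more broadly, as a comparison of two regimens given over two weeks.
- **Regimens.** Protocol 3.5.3 describes the active arms as "QD for both weeks or BID for the 1st week and QD the 2nd week". From the Day 8 AM dose their assigned dosing is identical. That dose is also the BID/QD arm's first single 40 mg dose (Protocol Table 2).
- **Orthostatic criteria.** In SAP 7.9.5, patients passing the three orthostatic "criteria at any postdose timepoint will also be summarized by treatment group".
- **Notable changes (Table 4).** SAP 7.9.5 presents by treatment group "The number and percentage of patients who had a notable change from baseline in BP and pulse" and names no window. SAP 9.1 adds: "All postbaseline assessments including unscheduled assessments, if any, will be used for notable value determination". Supine BP and pulse are also taken at the Day 21 and Day 42 visits, off drug (Protocol 3.8.3).
- **Hypotension category.** SAP 7.9.1: "TEAEs associated with hypotension or lowering of BP will be summarized by treatment group and presented in a data listing". No window is given, the TEAE definition has no end date, and AEs are collected to the End of Trial Visit (Protocol 3.7.3.9).
- **Contrast.** For TEAEs in general the SAP does split time: "TEAEs that started during Week 1 (study days 1-7) or Week 2 (study days 8-14) will be presented by treatment group". Protocol 3.9.3.4.1 likewise asks for a summary of the first 7 days.

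**The concern.** For a drug expected to lower blood pressure, the counts of patients with an orthostatic drop, a notable BP or pulse change, or a hypotension event are among the most direct tolerability measures. The BID start can differ from QD dosing only in Week 1. After that, the BID/QD arm meets the 40 mg single dose that the other arm has taken for a week. A count of patients with an event at any time mixes these two situations, and for Table 4 it also mixes in off-drug visits.

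Two things are at stake. A real Week 1 difference may look smaller in the pooled count. And if the pooled counts are equal, the reader cannot tell whether the BID start did nothing or moved events to the switch.

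**Working it through.** **Plan's own figures.** No event rate, power or effect size is stated, so there is no calculation to reproduce. The allocation is coherent: 26 × 5/13 = 10, 10, and 26 × 3/13 = 6.

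**1. Where the orthostatic readings fall (Protocol 3.8.2, after the first dose).**
- Before the Day 8 AM dose: Day 1, 6; Day 2, 6; Day 7, 3; Day 8 AM predose, 1. Total 16.
- From the Day 8 AM dose: Day 8, 3; Day 13, 4; Day 15, 1. Total 8.

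So 16 of 24 (67%) belong to the period of different regimens and 8 of 24 (33%) to the period after it. By calendar day, with the Day 8 predose reading placed in Week 2, the first share is 15 of 24 (62.5%). The SAP schedule shows no 8-hour reading on Day 1, which gives 15 of 23 (65%). Dropping the two optional standing readings 4 hours after the PM dose (Days 1 and 2) from the protocol list gives 14 of 22 (64%). The schedule tables as extracted may show postdose readings on Days 3-6, whereas Protocol 3.8.2.5 lists only a predose supine reading. Three orthostatic readings on each of those four days would give 28 of 36 (78%). The pool is mostly Week 1 on every count.

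**2. Dilution.** Let p1 be the Week 1 risk in an arm and p2 the later risk, independent of Week 1. Then

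P(ever) = 1 - (1 - p1)(1 - p2).

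If p2 is the same in both arms, the any-time difference is (p1 for QD/QD - p1 for BID/QD) × (1 - p2). All rates below are assumptions.

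| Week 1, QD/QD v BID/QD | Later risk p2 | Any time | Difference in points |
|---|---|---|---|
| 40% v 10% | 30% | 58% v 37% | 30 becomes 21 |
| 30% v 10% | 50% | 65% v 55% | 20 becomes 10 |
| 50% v 20% | 10% | 55% v 28% | 30 becomes 27 |
| 50% v 20% | 30% | 65% v 44% | 30 becomes 21 |
| 50% v 20% | 50% | 75% v 60% | 30 becomes 15 |

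If later events occur only in patients who already had one in Week 1, P(ever) = p1 and nothing is lost.

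**3. Postponement against no effect (assumed rates).**
- Postponed: QD/QD 30% then 10% gives 1 - 0.7 × 0.9 = 37%. BID/QD 10% then 30% gives 1 - 0.9 × 0.7 = 37%.
- No effect: both arms 30% then 10% gives 37% v 37%.

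The any-time counts are the same. The Week 1 counts are 30% v 10% in the first case and 30% v 30% in the second.

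**4. Precision.** For 5/10 v 2/10 the 95% Wald half-width is 1.96 × √(0.25/10 + 0.16/10) = 0.397, about 40 points. At assumed true rates of 50% v 20%, a two-sided Fisher test at 0.05 with 10 per arm detects the Week 1 difference 13% of the time. The pooled figure is 10%, 6% and 4% for p2 of 10%, 30% and 50%.

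**The case against.** The strongest reply is that the any-time count is itself a proper answer. Protocol 2 compares regimens over two weeks, and if BID dosing only moves events to Day 8, then tolerability over the course has not improved and equal counts are the right result. This stands. It is why the any-time total should be kept, and why Week 2 is not noise.

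A reader might infer that pooled counts cannot separate prevention from postponement. They can: under the assumed rates above, prevention gives 58% v 37% and postponement 37% v 37%. A Week 1 count alone would favour BID in both cases. What the pooled count cannot separate is postponement from no effect.

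A reader might also infer that Week 1 information is hidden. The documents do not support this. SAP 7.9.5 summarizes standing BP and pulse at each timepoint, Protocol 3.9.3.3.1 asks for orthostatic change at each postdose assessment, and the hypotension preferred terms in Appendix 1 fall within the weekly TEAE tables. Yet summaries at single timepoints do not give the number of patients who crossed a threshold at some point in Week 1. Nor do preferred-term rows add up to patients with any hypotension event, because one patient can appear under several terms (SAP 9.2). The hypotension listing would allow that count to be built, but without a prespecified window.

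For Table 4 the pooling is partly inferred: SAP 9.1 says which readings are eligible, not how the table is laid out, and the table specifications are in a separate document (SAP 1). A split may exist there. Finally, the study is exploratory and descriptive with 10 patients per active arm, so a split will not make the comparison precise. That is also correct.

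**Conclusion.** The point holds in a limited form. The orthostatic count is pooled by explicit wording. The Table 4 count has no stated split and draws on all postbaseline readings, off-drug visits included. The grouped hypotension count has no stated window, although its component terms are shown by week. None of the three gives a prespecified count of patients with an event while the active regimens differed.

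Dilution is possible, not certain. Under equal and independent later risk it removes a fraction p2 of the Week 1 difference: 10% at p2 = 0.1, 30% at 0.3, 50% at 0.5. It is zero if later events only recur in patients already counted. The documents give no rates and no support for or against independence, so no single figure can be defended. The claim that a benefit of the BID start is hidden goes further than the documents allow. This is an inexpensive improvement to how the counts are reported, not a flaw that invalidates the analysis.

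**What to change.** In SAP 7.9.5 (orthostatic criteria and Table 4) and in 7.9.1 with Appendix 1 (grouped hypotension category), report patient counts by treatment group for:

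- (a) first dose to just before the Day 8 AM dose;
- (b) Day 8 AM dose through Day 15;
- (c) follow-up, where measured (for BP and pulse, supine readings only);
- the any-time total, kept as the whole-course comparison.

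Name (a) as the BID-versus-QD contrast and (b) as the post-switch contrast, both descriptive. Give each window its own denominator, namely patients observed in it. State how an event on Day 8 without a start time is assigned, since the weekly TEAE tables cut by study day. If the table specifications already contain this split, a sentence in the SAP is enough.

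The cost is SAP wording, to be settled before unblinding, and a period variable in three tables. No new data are needed. The downside is small cells: with about 10 patients per active arm, each estimate remains imprecise and should be read with its interval.
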